1. STUDY OBJECTIVES

1.1 **Primary Study Aims:** Determine the feasibility of an integrated psychosocial treatment (ACT + MBRP) in veterans with chronic pain with evidence of opioid-related problems. Chronic pain patients ($n = 120$) who are receiving opioid therapy and who are identified as opioid misusing, abusing, or dependent will be recruited from the Albuquerque Veterans Administration (VA) Hospital. Participants will be randomized to receive standard care or standard care in addition to ACT+MBRP. **Hypothesis 1: Feasibility of recruitment:** Given the high prevalence of both chronic pain and opioid-related problems in VA populations, we hypothesize it will be possible to recruit our target sample size ($n = 120$) within a 15-18 month timeframe. **Hypothesis 2: Feasibility of retention:** Drop-out rates will be consistent with other trials of similar psychosocial interventions for chronic pain (i.e., < 20%^{5,21-23}).

1.2 **Secondary Study Aims:** To examine weekly progress on specific therapy targets (e.g., pain acceptance, self-compassion, opioid craving) in the interventions in order to identify potential mechanisms of change and to identify the choice of intermediate endpoints for a larger randomized clinical trial.

Hypothesis 1: Evidence of treatment mechanisms: The combined ACT+MBRP treatments will be associated with changes in treatment mechanisms specified within the therapeutic models and in a manner consistent with that of previous work on ACT and MBRP, in comparison with standard care.

Hypothesis 2: Selection of intermediate endpoints: Weekly progress measures will provide data indicating measures of treatment-specific mechanisms that are most sensitive to change. We hypothesize that acceptance of pain discomfort will be most sensitive to change in ACT and that reductions in reactivity to substance craving will be most sensitive to change in MBRP.

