5. STUDY INTERVENTIONS

5.1 Interventions, Administration, and Duration

Intervention Conditions—All participants will continue to receive standard care for chronic pain within the VA. In addition, one-half of participants will be randomized to also receive ACT plus MBRP.

Standard Care: All conditions will also receive standard treatment as usual, as indicated by treatment plan and not manipulated by the research team. Consistent with national and VA standards^{14,15}, care at the recruitment sites typically consists of noninvasive interventions, such as analgesic pain medications (e.g., opioids, NSAIDs, anti-epileptics), topical solutions (e.g., lidocaine), physical therapy, and massage, as well as limited invasive interventions (e.g., injections, radiofrequency denervation).

Acceptance and Commitment Therapy (Weeks 2–9): The ACT intervention is based on the standardized and manualized protocol of [name] and Sorrell¹⁶, which consists of weekly 90-minute group meetings over eight weeks. The protocol has been successfully used in previous clinical trials (e.g.,^{17,18}) and is currently available on the VA's Evidence-Based Practice Sharepoint website. Over the course of the group meetings, participants will identify areas of meaningful functioning that have been adversely impacted by pain, learn methods to enhance pain willingness in the service of these meaningful areas, and practice present-focused awareness skills. Group sessions will include discussions of the impact of pain and distress avoidance, identify alternative to this avoidance and establish plans for behavior change, demonstration and role-playing exercises, and homework assignments. Participants will be provided with a treatment manual to help guide and inform practice outside of group sessions. Table 1 provides an outline of session content for the eight week ACT intervention. We anticipate enrolling approximately eight patients per group.

Table 1: Overview of ACT Treatment Sessions

Session	Objectives and Content
1	
a. Treatment orientation and overview.b. Review treatment history and evaluate it in terms of how it has worked relative to patient's goals and expectations.

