Analyses to Test Secondary Aim Hypotheses. The primary goal of Aim 2 is to identify potential mechanisms of change and intermediate endpoints for future randomized clinical trials comparing ACT+MBRP to standard care. We will accomplish this goal by examining initial level and changes in targeted mechanisms over time during the course of treatment, as well as the association between changes in targeted mechanisms during treatment and 6-month follow-up measures of clinical outcomes. Targeted mechanisms will include (1) pain acceptance (2) psychological flexibility, (3) experiential avoidance, (4) opioid craving, and (5) reactivity to pain and craving, and will be examined using latent growth curve models with fixed effects of treatment and random effects of time. These analyses will provide an estimate of the initial level of each targeted mechanism (i.e., intercept) and the change in the targeted mechanisms over time (slope). Clinical outcome measures will include pain interference, pain behavior, and opioid misuse and will be examined using mediation analyses within the context of latent growth curve modeling⁶⁴, as we have done in prior studies^{63,65}. Specifically, as shown in simplified form in Figure 2, we will examine whether initial level (intercept) or changes (slope) in the targeted mechanisms ("M" in figure 2) during treatment mediate the effect of treatment on 6-month clinical outcomes, controlling for baseline levels of the outcomes. These analyses will also provide a test of Aim 2 Hypothesis 2, which is to identify those measures that are most sensitive to change (measures with the largest slope). Identifying measures that are more sensitive to change will help us in identifying intermediate endpoints for a larger RCT. Validation of intermediate endpoints is challenging and it is often recommended that meta-analytic methods be used⁶⁶, but alternative methods have been developed that allow for the evaluation of endpoints in mental-health clinical trials⁶⁷.

Figure 2. Simplified mediation model (excludes residual terms and covariances)

models will be estimated using the product of coefficients method⁶⁸, which provides an estimate of the mediated effect by multiplying regression coefficients for the regression of the mediators (e.g., slope of targeted mechanism) on treatment condition (i.e., a-path or α) and for the regression of the clinical

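### Aim 2 Hypothesis 2 is phase-specific, but it is tested by ranking whole-course slopes with no common scale, direction or named arm contrast

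*Combined protocol and SAP*

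**What the plan says.** Section 1.2 lists as examples of what is tracked weekly "specific therapy targets (e.g., pain acceptance, self-compassion, opioid craving". Hypothesis 2 then makes two predictions, one per treatment component: "acceptance of pain discomfort will be most sensitive to change in ACT", and "reductions in reactivity to substance craving will be most sensitive to change in MBRP".

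Both components go to the same arm, one after the other. Section 5.1 heads the first "Acceptance and Commitment Therapy (Weeks 2–9" and places MBRP in weeks 10–13. There is no ACT-only or MBRP-only arm, so only time can separate the components.

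Section 9.1 fits a latent growth curve to each mechanism, with an intercept for initial level and a single parameter for "the change in the targeted mechanisms over time (slope". The same analyses are to test Hypothesis 2, in order to "identify those measures that are most sensitive to change (measures with the largest slope". For mediation, Section 9.1 also estimates the a-path, the "regression of the mediators (e.g., slope of targeted mechanism) on treatment condition". The mechanisms listed are pain acceptance, psychological flexibility, "3) experiential avoidance, (4) opioid craving, and (5) reactivity to pain and craving". Self-compassion is not in that list.

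The only transformation mentioned in Section 9.1 is one to bring distributions closer to normal.

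**The concern.** Aim 2 is meant to help choose intermediate endpoints for a larger trial. The ranking rule leaves three things open that can change its result.

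- **Metric and direction.** The weekly questionnaires differ in length and response range, and no common scale is named. Acceptance should rise and craving should fall, so the largest slope is not defined until scores are aligned.
- **Phase.** A component-specific hypothesis is examined with a slope described for treatment as a whole.
- **Contrast.** The rule does not say whether it ranks the slope in one arm, the slope over both arms, or the difference between arms. A measure that improves equally under standard care could rank high on its own slope, yet say nothing about the intervention.

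A measure could therefore be carried into the next trial because of how it is scored or when it changes, and not because the intervention moves it.

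**Working it through.** The plan states no power, alpha or sample size for this ranking, so there is no figure of its own to reproduce.

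**1. Effect of scoring.** Item counts and response options come from Section 6.2.4 and Appendix IV; no scoring rule is given. Score ranges, as sum or item mean:
- CPAQ: 20 items scored 0–6, so 20 × 6 = 120, or 6.
- SCS: 26 items scored 1–5, so 26 × 4 = 104, or 4.
- PACS: 5 items scored 0–6, so 5 × 6 = 30, or 6.

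Assume every measure changes by 10% of its range over 12 weeks. Slope per week = 0.10 × range / 12.

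| | CPAQ | SCS | PACS |
|---|---|---|---|
| Sums | 1.00 | 0.87 | 0.25 |
| Item means | 0.050 | 0.033 | 0.050 |

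For the same proportional change, CPAQ against PACS is 4:1 or 1:1, and SCS is second or last.

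**2. Effect of one slope over two phases.** Take 13 equally spaced weekly points (week 1 as baseline, then weeks 2–13) and a least-squares line. The mean week is 7 and the sum of squared deviations is 182.
- One unit of change spread evenly over ACT, then flat: slope = 16.5/182 = 0.0907. The slope within the ACT phase is 1/8 = 0.125. Share kept: 0.0907/0.125 = 73%.
- Flat through ACT, then one unit spread evenly over MBRP: slope = 12.5/182 = 0.0687. The slope within the MBRP phase is 1/4 = 0.250. Share kept: 0.0687/0.250 = 27%.

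For equal total change, the whole-course slope puts the ACT-phase measure ahead (0.0907 against 0.0687), while the phase-specific weekly slopes put the MBRP-phase measure ahead (0.250 against 0.125). An MBRP-only change must be 0.0907/0.0687 = 1.32 times as large to tie on the whole-course slope.

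**3. Precision of a two-piece model.** Inputs from Section 9.2: 60 per arm and correlation 0.43 (given there for three assessments; applying it to weekly data is an assumption). With random intercepts only,

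SE of between-arm change = phase weeks × k × √(2 × (1 − 0.43)/60) = phase weeks × k × 0.138,

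where k is the slope SE per unit residual SD for one person: 0.1196 (ACT piece) and 0.2586 (MBRP piece) with a knot at week 9, and 1/√182 = 0.0741 for one slope.
- ACT: 8 × 0.1196 × 0.138 = 0.132 SD.
- MBRP: 4 × 0.2586 × 0.138 = 0.143 SD.
- Single slope: 12 × 0.0741 × 0.138 = 0.123 SD.

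A between-arm change detectable with 80% power is 2.80 × SE: 0.37 SD for ACT and 0.40 SD for MBRP. Section 9.2 cites MBRP effects of 0.21 to 0.52.

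Section 9.1 specifies random effects of time. Suppose true change varies between people with SD 0.5 in each phase (assumed). The phase SEs become 0.160 and 0.169. The single-slope SE is 0.153 if whole-course change also has SD 0.5, which implies phase changes correlated at about −0.5. It is 0.175 if the phase changes are independent: √[(0.451 + 144 × (0.0907² + 0.0687²) × 0.25) × 2/60], where 0.451 = (12 × 0.0741)² × 0.57. Whether splitting the slope loses precision thus depends on that correlation.

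**The case against.** The strongest reply is that much of the material is already in the plan, and that the ranking is one input among several.

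- **The arm contrast is estimated.** A reader might infer that treatment effects on slope are ignored. They are not: the a-path is that effect, and the analyses said to test Hypothesis 2 include it. What is missing is a sentence making it the ranked quantity.
- **The rule is worded in the plural.** A reader might infer that one ranking can name only one winner and so must contradict a hypothesis with two. Section 9.1 speaks of measures, so two leading measures are compatible with it. The problem is that neither is identified within its own phase.
- **Constructs may be covered by collected items.** A reader might infer that psychological flexibility, experiential avoidance and reactivity are unmeasured. The weekly diary in Appendix IV asks about willingness to have pain and distress, effort to make unpleasant experiences go away, and effective action. PACS item 4 asks how hard drugs or alcohol would be to resist. These are plausible proxies. What the documents lack is an assignment of items to constructs.
- **Linearity is inferred.** The text describes one slope but does not call it linear, and Figure 2 is not shown. The phase arithmetic depends on this reading; the points on metric and contrast do not.
- **This is a secondary aim of a feasibility study.** Section 9.1 says the ranking will help identify endpoints, and the mediation results also inform the choice. That limits the damage, but does not make the rule well defined.

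**Conclusion.** The concern stands. As written, the rule can order measures by scoring width (4:1 or 1:1 for CPAQ against PACS under the same proportional change), leaves direction undefined, and tests neither half of Hypothesis 2 in its own phase. The 73% and 27% figures assume one linear slope, 13 equally spaced points, and change that is linear within one phase and absent outside it. The scoring figures assume simple sums or item means.

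A reader might go further and infer a rate at which the rule picks the wrong measure. The documents do not support one: Hypothesis 2 does not predict that craving outranks acceptance over the whole course, so a whole-course order with acceptance first is not an error under it. Any such rate would also depend on unstated assumptions about change outside each measure's own phase and about how many measures compete.

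The change should be made before slopes are examined. It does not affect the primary feasibility aim.

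**What to change.** Replace the largest-slope rule in Section 9.1 with the following.

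1. Rank measures by the between-arm difference in slope (the a-path), divided by the pooled baseline SD or another prespecified standardiser, with scores oriented so that improvement is positive.
2. Estimate it from a two-piece growth curve with the knot at the end of ACT, and rank within each phase, with confidence intervals.
3. State the time origin in both arms. Section 4.3 randomises straight after baseline and expects most participants to wait up to about a month for a group, and standard care has no session clock. Study week 9 therefore need not be the end of ACT for every participant.
4. Read the MBRP-phase ranking as MBRP after ACT, including any carry-over, and label it exploratory.
5. State which collected items (CPAQ, SCS, PACS, weekly diary) represent psychological flexibility, experiential avoidance and reactivity, and include self-compassion in the ranking.
6. If the baseline SD is the standardiser, confirm that CPAQ, SCS and PACS are collected at Day 0. The schedule in Section 6.1 marks weekly assessments there, but the baseline list in Section 6.2.2 omits them.

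**Cost.** No new data are needed, provided existing items are accepted for the three constructs. Weekly assessments are planned for participants generally (Section 3) and budgeted for 64 + 56 = 120 people (Section 6.2.5.1). Each mechanism needs one more slope factor. With random intercepts only, precision falls modestly, from an SE of 0.123 SD for the single slope to 0.132 SD (ACT) and 0.143 SD (MBRP). With random slopes, the comparison depends on the correlation between phase changes. Either way, the MBRP-phase ranking will be imprecise at this sample size.

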9.2 Sample Size and Randomization

Commented [KV4]: Blocking

Statistical Power for Secondary Aims: We estimated statistical power for the mediation analyses using parameter estimates from prior studies of mediation following ACT for chronic pain⁵ and following MBRP for substance use disorders^{7,63} to estimate the effect sizes for the behavioral measures in the current study. Following ACT, numerous behavioral measures significantly mediated changes in disability, depression, pain-related anxiety, medical visits, and number of classes of prescribed analgesics, with large mediation effect sizes. The prior studies of MBRP have found that experiential avoidance, awareness, and nonjudgment significantly mediated the association between treatment and changes in craving ($\alpha = 0.56$; $\beta = -0.43$) and that craving significantly mediated the association between treatment and changes in substance use ($\alpha = -0.20$; $\beta = 0.71$). Based on these effect sizes and power estimates for testing mediation derived from a simulation study⁷¹, we will have power greater than 0.80 to detect significant mediating effects with the proposed sample size of 120.

Examining mechanisms of change assumes that treatment influences change in the clinical outcome measures at follow-up, thus we also estimated the power to detect a main effect of treatment on the clinical outcome measures. Effect size estimates were drawn from prior studies of ACT for patients with chronic pain^{5,23,60,72} and MBRP for substance use disorders^{52,63,73}. The effect sizes for ACT in comparison to treatment as usual or active treatment for chronic pain have ranged from 0.29 to 1.09. The effect sizes for MBRP in comparison to treatment as usual for substance use and craving have ranged from 0.21 to 0.52. Based on these studies, we estimate a minimum average effect size of $d=0.25$. Using a mixed-effects linear model with $\alpha=0.05$ (two-tailed test), three repeated assessments (baseline, end of treatment, 6-month follow-up), and a correlation among repeated measures of 0.43 (based on prior studies) we will need 60 subjects per condition (total $n = 120$) for 80% power to detect a main effect of ACT+MBRP in comparison to standard care.

Treatment Assignment Procedures

We will use a random order variable-sized block randomization procedure with block sizes of 2, 4, and 6. The investigators will be blind to the size of each block and randomization allocation.

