outcome on the mediators (i.e., b-path or β). We will use bootstrapping to obtain 95% confidence intervals of the mediated effect⁶⁹. We will use maximum likelihood estimation for all analyses, which provides the variance-covariance matrix for all available data and is the preferred method for estimation when some data are missing⁷⁰. Attrition analyses will determine whether there are any differences in study variables between those with missing and complete data. Study variables associated with missing data will be covaried in all analyses.

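### Power above 0.80 for mediation at n = 120 is not delivered by the craving coefficients quoted as its basis, and the scale of the coefficients is not stated

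*Combined protocol and SAP*

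**What the plan says.** The claim is in section 9.2, under the heading on statistical power for the secondary aims. The inputs are described as obtained "using parameter estimates from prior studies of mediation". For Acceptance and Commitment Therapy (ACT) no coefficients appear; mediation is reported for several outcomes, ending with "number of classes of prescribed analgesics, with large mediation effect sizes". For MBRP two pairs are given:

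- experiential avoidance, awareness and nonjudgment as mediators of craving: α = 0.56, β = −0.43;
- craving as mediator of substance use: α = −0.20, β = 0.71.

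The conclusion opens "Based on these effect sizes and power estimates for testing mediation derived from a simulation study" and ends "we will have power greater than 0.80 to detect significant mediating effects with the proposed sample size of 120".

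Section 9.1 gives the analysis. The mediated effect is a product of coefficients, where α comes from the "regression coefficients for the regression of the mediators (e.g., slope of targeted mechanism) on treatment condition" and β from the regression of the clinical outcome on the mediator. The test is an interval: "We will use bootstrapping to obtain 95% confidence intervals of the mediated effect".

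Neither section says whether α and β are standardised, how treatment was coded, what the residual SDs were, or what power belongs to which pair.

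**The concern.** The power statement rests on the quoted effect sizes and covers mediating effects generally, yet the two pairs differ greatly in their α paths. An indirect effect can hardly be detected more often than its weaker path. For craving that is the path from treatment, at −0.20, and on either usual effect-size scale 120 participants are too few for it.

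Craving is a targeted mechanism in section 9.1, is measured weekly, and is central to the MBRP part of the second secondary hypothesis in section 1.2. A reader who trusts the stated power could take a null craving result as evidence against that mechanism. On the quoted coefficients such a result would occur in about 40% or about 80% of trials in which the effect was real.

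**Working it through.** **Inputs.** From section 9.2: n = 120, 60 per arm, and the pairs (0.56, −0.43) and (−0.20, 0.71). From section 9.1: product of coefficients with a 95% bootstrap interval, so two-sided 0.05. From section 1.1: drop-out below 20%, used only for a sensitivity check at 120 × 0.8 = 96. Assumed: one mediator measured once, no direct effect.

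**Scales tried.** (i) Standardised: α is the treatment–mediator correlation, variables have unit total variance. (ii) SD difference: treatment coded 0/1, unit residual SDs. (iii) Raw: residual SD unknown, so shown over a range.

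**Step 1: the α path alone.** This is a two-sample t test with 118 degrees of freedom and noncentrality d × √(n/4) = d × √30 = 5.477d.

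- Craving, standardised: d = 2 × 0.20 / √(1 − 0.04) = 0.408, noncentrality 2.24, power 0.602.
- Craving, SD difference: d = 0.20, noncentrality 1.10, power 0.192.
- Other pair, SD difference: d = 0.56, noncentrality 3.07, power 0.860. Standardised, it is above 0.99.

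The smallest d with 80% power at n = 120 is 0.516, which is 0.250 as a standardised coefficient. The craving α is below both limits. Reaching 80% on that path would take about 192 participants in total (standardised) or 788 (SD difference).

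**Step 2: the indirect effect at n = 120, by simulation.** Joint significance used 10,000 trials; the percentile bootstrap used 1,500 trials of 500 resamples.

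| Pair | Test | Standardised | SD difference |
|---|---|---|---|
| (0.56, −0.43) | joint significance | 0.987 | 0.854 |
| (0.56, −0.43) | percentile bootstrap | 0.977 | 0.877 |
| Craving (−0.20, 0.71) | joint significance | 0.599 | 0.197 |
| Craving (−0.20, 0.71) | percentile bootstrap | 0.641 | 0.218 |

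The plan's figure is therefore reproduced for the first pair and not for craving. The Sobel test, which is not planned, gives 0.79–0.81 for the first pair as an SD difference and 0.59 / 0.18 for craving. The β path of 0.71 has power near 1, so nothing can be gained there.

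**Step 3: 20% loss.** At n = 96 (an approximate lower bound, since maximum likelihood uses partial records) craving has power 0.50–0.54 standardised or 0.15–0.18 as an SD difference. The other pair has 0.95–0.96 or 0.76–0.77.

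**Step 4: raw coefficients.** Power of the α path at n = 120 is that for d = |α| / SD, where SD is the mediator's residual SD:

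| Mediator residual SD | Craving, 0.20 | Other pair, 0.56 |
|---|---|---|
| 0.30 | 0.95 | >0.99 |
| 0.35 | 0.87 | >0.99 |
| 0.5 | 0.58 | >0.99 |
| 1.0 | 0.19 | 0.86 |
| 1.5 | 0.11 | 0.53 |
| 2.0 | 0.08 | 0.33 |

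The 80% limits are 0.20 / 0.516 = 0.39 for craving and 0.56 / 0.516 = 1.09 for the other pair. If β is raw, the β path also needs an outcome-to-mediator residual SD ratio of at most about 2.7 (craving) or 1.65 (other pair). The plan gives none of these SDs.

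**The case against.** The strongest reply is that −0.20 may be a raw growth-model coefficient. Section 9.1 defines α with a slope as its example, section 9.2 calls its inputs parameter estimates, and one earlier MBRP trial is cited both for the modelling approach and for the coefficients. A residual SD below 0.39 is not far-fetched for a weekly slope: 0.39 × 12 weeks is about 4.7 points, roughly 16% of the 0–30 range if the five craving items (0–6 each) are summed, though most of the range if they are averaged. Scoring and time unit are assumptions here. This stands as a possibility, and on this reading the claim is unsupported rather than wrong. It does not rescue the sentence, which speaks of effect sizes and gives no SD.

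Second, the trial will fit a latent growth model with weekly measures and baseline control, not the model used here. That is true, and extra precision could raise power. Section 9.2 does not invoke it for the mediation figure. For scale, covariates would have to explain about 37% (standardised) or 85% (SD difference) of the mediator's residual variance to bring the craving α path to 80%.

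Third, the cited simulation study or the ACT effects may be the real basis, or only the first pair may be meant. The simulation tables and the ACT coefficients are not in the documents, and the text does not limit the claim.

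Fourth, a cap set by the α path applies strictly to joint significance, and the bootstrap slightly exceeds it. That is correct, but 0.64 and 0.22 remain well below 0.80.

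**Conclusion.** The concern holds. Read as the effect sizes that section 9.2 calls them, the quoted coefficients give power above 0.80 for (0.56, −0.43) but only about 0.6 (standardised) or about 0.2 (SD difference) for craving. If they are raw, the figure cannot be verified for either pair. These results rest on a single-mediator model with no direct effect, two-sided 0.05 and complete data; the planned latent growth model was not simulated.

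The consequence is modest. Mediation is a secondary aim of a feasibility trial. Section 9.1 plans to "identify those measures that are most sensitive to change (measures with the largest slope"), reports confidence intervals, and drops no measure for a non-significant mediated effect. Section 9.2 justifies n = 120 separately by a main-effect calculation. The statement should be corrected, but the design does not depend on it.

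**What to change.** In section 9.2, state the scale of α and β and the treatment coding, with the mediator and outcome SDs if the coefficients are raw. Then replace the general claim with power for each pathway, labelled as a single-mediator approximation:

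- If α is standardised: at n = 120, power is about 0.98 for (0.56, −0.43) and about 0.6 for craving (−0.20, 0.71).
- If α is an arm difference in SD units: about 0.85 and about 0.2.
- If raw: the SDs used and the power that follows for both pairs.

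Keep the figure above 0.80 only for pathways that support it, and give the ACT coefficients if they are part of the basis. Power with 20% loss (n = 96, labelled an approximate lower bound) could be added: about 0.96 and 0.50–0.54 standardised, or 0.76–0.77 and 0.15–0.18 as an SD difference.

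The cost is protocol wording and a less favourable stated power. No participants are added, the analysis does not change, and no new rule of interpretation is needed.

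### Section 9.2 claims mediation power above 0.80 without qualification, but its quoted coefficients do not support this for the mediator-outcome paths in section 9.1

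*Combined protocol and SAP*

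**What the plan says.** Section 9.1 (Analyses to Test Secondary Aim Hypotheses) sets out the Aim 2 mediation models. There are five mechanisms: pain acceptance, psychological flexibility, experiential avoidance, and "4) opioid craving, and (5) reactivity to pain and craving". Their intercepts and slopes during treatment are the mediators. For the other end of the model, "Clinical outcome measures will include pain interference, pain behavior, and opioid misuse". The mediated effect is the product of the two path coefficients, with a 95% bootstrap interval.

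Section 9.2 (Statistical Power for Secondary Aims) supports the sample size with three pieces of prior evidence:

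- After ACT, "numerous behavioral measures significantly mediated changes in disability, depression, pain-related anxiety, medical visits, and number of classes of prescribed analgesics". The effects are described as large and no coefficient is given.
- In MBRP studies, experiential avoidance, awareness and nonjudgment "significantly mediated the association between treatment and changes in craving", with coefficients 0.56 and -0.43.
- In MBRP studies, craving mediated the treatment effect on substance use, with coefficients -0.20 and 0.71.

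The conclusion follows: "Based on these effect sizes and power estimates for testing mediation derived from a simulation study", "we will have power greater than 0.80 to detect significant mediating effects with the proposed sample size of 120". The scale of the coefficients and the coding of treatment are not stated, and no allowance for loss to follow-up appears in this paragraph.

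**The concern.** Power for a mediated effect belongs to a particular pair of paths: treatment to mediator, and mediator to outcome. Section 9.2 quotes paths to seven outcomes: five from ACT, plus craving and substance use from MBRP. None of the seven is named as a mediation outcome in section 9.1, and one of them, craving, is a mediator there. The sentence on power makes no distinction among paths, so a reader would take 0.80 to apply to every planned mediation test.

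Aim 2 is meant to identify mechanisms and intermediate endpoints for a larger trial. A stated power above 0.80 makes a non-significant mediated effect look informative. If the true power for a path is nearer 0.6 or 0.2, such a result says little, and a useful mechanism could be set aside.

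**Working it through.** **Inputs.** From section 9.2: N=120, 60 per arm; pair 1 = (0.56, -0.43), product -0.241; pair 2 = (-0.20, 0.71), product -0.142. From section 9.1: product of coefficients with 95% bootstrap interval, so two-sided 0.05. From section 1.1: drop-out below 20%, used only for a sensitivity case of 120 × 0.80 = 96.

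**Match of paths.**

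| Prior evidence in 9.2 | Coefficients | Counterpart in 9.1 |
|---|---|---|
| ACT, five outcomes | none quoted | none among the 9.1 mediation outcomes |
| Mindfulness processes to craving | 0.56, -0.43 | first path yes (experiential avoidance); second path no (craving is a mediator) |
| Craving to substance use | -0.20, 0.71 | close analogue of opioid craving to opioid misuse |
| Any path to pain interference or pain behavior | none quoted | two of the three planned outcomes |

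**Power from the quoted pairs.** The model was M = aX + e₁, Y = bM + e₂, with one observed mediator and no direct effect. Simulation used 2,000 replicates, each with 500 bootstrap resamples, and both percentile and bias-corrected intervals. Because the scale is not given, three were tried: fully standardized; treatment coded -1/+1 with residual SD 1; and treatment coded 0/1 with residual SD 1.

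Bootstrap power (percentile / bias-corrected):

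| Pair | N | Standardized | -1/+1 | 0/1 |
|---|---|---|---|---|
| 1 (0.56, -0.43) | 120 | 0.99 / 0.99 | 0.99 / 0.99 | 0.86 / 0.88 |
| 1 | 96 | 0.96 / 0.97 | 0.98 / 0.99 | 0.77 / 0.83 |
| 2 (-0.20, 0.71) | 120 | 0.63 / 0.64 | 0.60 / 0.62 | 0.20 / 0.23 |
| 2 | 96 | 0.52 / 0.53 | 0.50 / 0.53 | 0.18 / 0.20 |

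Pair 1 therefore reproduces the plan's figure at N=120. The joint-significance test gives 0.85 at worst. The Sobel test under 0/1 coding gives 0.78, but it is not the planned test. Pair 2 does not reach 0.80 on any scale or test tried. Even one-sided, its highest figure is 0.73.

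**Check on pair 2 by hand.** The limiting step is the treatment-to-craving path.

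- Standardized: SE = √((1 - 0.20²)/120) = 0.0894, so 0.20/0.0894 = 2.24. Power ≈ Φ(2.24 - 1.96) = 0.61.
- 0/1 coding: SE = √(2/60) = 0.183, so 0.20/0.183 = 1.10. Power ≈ Φ(1.10 - 1.96) = 0.19.

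For 80% power on this path alone, about 189 analysed participants are needed on the standardized scale, from (1.96 + 0.84)² × 0.96/0.04. Under 0/1 coding the number is about 786.

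**What n=120 can detect where no coefficient is quoted.** The assumptions are mine: joint significance, 60 per arm, slope observed without error, participants independent, Fisher z for the second path with three covariates. Power is the product of the two path powers.

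- 0.52 SD shift in slope, partial correlation 0.4: 0.806 × 0.995 = 0.80.
- 0.60 SD shift in slope, partial correlation 0.3: 0.903 × 0.911 = 0.82.

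**The case against.** Borrowing from related outcomes is normal in a pilot. Section 2.2 notes that the combination has not been studied directly, so coefficients for the exact paths could not be expected. Section 9.2 says openly that prior estimates are being carried over. Disability is an outcome of the trial, measured with the Sickness Impact Profile, although section 9.1 does not list it for mediation. The aim is secondary and the primary outcomes are descriptive. All of this stands. It limits the seriousness of the point but does not supply support for an unqualified 0.80.

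Four stronger readings are tempting, and the documents do not support them.

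- *The prior paths are all foreign to the trial.* Craving to substance use is a close analogue of a planned path. The 0.56 in pair 1 includes experiential avoidance, a listed mechanism. Only the second path of pair 1 falls outside the plan, so the pair should not simply be deleted.
- *Mediation power is capped at 27%.* That is the power of a two-group comparison with 60 per arm and a shift of 0.25 SD. Section 9.2 gives 0.25 as a minimum average effect on clinical outcomes, not on mechanism slopes. The power of the first path is an exact ceiling for joint significance but not for a bootstrap interval. With a=0.25 and b=0.43, a simulation gave 0.28 for the first path, 0.29 by percentile and 0.34 by bias-corrected bootstrap.
- *A null result will be taken as evidence against a mechanism.* No section says so. Section 9.1 ranks sensitivity to change by the size of the slope, and bootstrap intervals are already planned. The misreading is a risk that the power statement invites, not a stated rule.
- *Power is shown to be low for pain interference and pain behavior.* It is not shown either way, because no coefficient is quoted. The ACT study and the simulation study that the plan cites may contain more, but they cannot be checked from the documents.

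**Conclusion.** The point holds as a limited one. The general claim of more than 0.80 is supported only by a coefficient pair whose second path is not in section 9.1. For the one quoted pair that resembles a planned path, power at n=120 is about 0.60 to 0.64 with unit-variance treatment, or 0.20 to 0.23 under 0/1 coding. With 20% loss it is about 0.50 to 0.53, or 0.18 to 0.20. For pain interference and pain behavior the claim has no quoted coefficient behind it.

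These figures depend on the unstated coefficient scale, which is why a range is shown. They use a single observed mediator in place of a latent growth slope, no direct effect and independent participants. The conclusion that pair 2 stays below 0.80 holds for every scale and test tried. The issue is worth correcting before analysis, but it does not touch the primary feasibility aim.

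**What to change.** In section 9.2:

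1. Withdraw the unconditional statement of power above 0.80.
2. State the scale of the quoted coefficients and the coding of treatment.
3. Give power by mediator-outcome path. Restate craving to misuse at the lower figure that follows from (-0.20, 0.71) on the stated scale, with and without 20% loss. Keep 0.56 only as evidence on the treatment-to-mechanism path for experiential avoidance.
4. For paths without a prior coefficient, state what n=120 can detect with 80% power and label the assumptions, for example the two combinations of slope shift and partial correlation worked out above.
5. State that mediated effects will be reported as estimates with their bootstrap intervals, and that non-significance will not be read as absence of mediation.

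The 27% figure at 0.25 SD should not be presented as a bound on the planned bootstrap test.

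The cost is a few sentences and a less favourable stated power. No patients, data or analyses are added.
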